## DEFINITION OF TERMS

Corticosteroid-Free Remission	EBS remission with no corticosteroid use for at least 6 months prior to Week 58 among subjects who are on corticosteroid at Baseline
EBS Remission	An endoscopic subscore of 0 or 1, rectal bleeding subscore of 0, and at least a one point decrease in stool frequency from baseline to achieve a subscore of 0 or 1
Endoscopic Response	Endoscopic subscore of 0 or 1
Geboes histologic remission	Based on the Geboes Scale, all of the following must be met to be considered in Geboes histologic remission. Grade 0        ≤ 0.3 Grade 1        ≤ 1.1 Grade 2a       ≤ 2A.3 Grade 2b       2B.0 Grade 3        3.0 Grade 4        4.0 Grade 5        5.0
Mayo Clinic Score*	Composed of sub-scores from endoscopy, rectal bleeding, stool frequency, and PGA
Mayo Clinic Score Remission	MCS of ≤ 2 points and no individual subscore > 1 point
Mayo Clinic Score Remission (Alternative Definition)	Rectal bleeding, stool frequency, and PGA subscore of 0 and an endoscopic subscore of 0 or 1; overall MCS of ≤ 1
Mayo Clinic Score Response	A Mayo Clinic Score (MCS) reduction of ≥ 3 points and at least 30% from baseline score with an accompanying decrease in rectal bleeding subscore of ≥ 1 point or an absolute rectal bleeding subscore of 0 or 1
Partial Mayo Clinic Score	Composed of sub-scores from rectal bleeding, stool frequency, and PGA

\* Rectal bleeding and stool frequency subscores will be rounded to the nearest integer for determination of eligibility and calculation of endpoints

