## 1. INTRODUCTION

### 1.1. Background

Ulcerative colitis (UC) is a chronic, intermittent, relapsing disease characterized by inflammation of the colonic mucosa, which is limited to the colon and rectum. The disease characteristically commences in the rectum and may extend proximally in an uninterrupted pattern into the colon. It can involve the entire colon (pan-colitis), the left colon, or isolated recto-sigmoid disease with patients being equally distributed in those 3 phenotypes. In the United States (US), the prevalence of UC has been estimated to be 238 per 100,000 adults {Kappelman 2007}. Europe has the highest reported prevalence values for inflammatory bowel disease (IBD; 505 per 100,000 persons for UC and 322 for Crohn's Disease [CD]). The annual incidence of UC is 24.3 per 100,000 person-years in Europe and the incidence is 6.3 per 100,000 person-years for UC in Asia {Molodecky 2012}. The incidence and prevalence of IBD appear to be increasing over time globally. The hallmark symptoms of the disease are bloody diarrhea, rectal urgency, and tenesmus. The clinical course tends to wax and wane with periods of remission interspersed with periods of active disease. Ulcerative colitis may also be associated with extra-intestinal manifestations including ocular lesions, skin lesions, arthritis, and primary sclerosing cholangitis. The exact pathophysiology is not known but in general, genetic predisposition in conjunction with environmental and social factors (such as history of tobacco use, medication history, and geography) may impact development of disease. Discoordinated activity of both innate and adaptive immune responses in combination with epithelial barrier defects and dysbiosis lead to an inflammatory cascade resulting in clinical signs and symptoms of UC {Ungaro 2016}.

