Induction	Exploratory	MCS response at Week 10	An MCS reduction of ≥ 3 points and at least 30% from baseline score with an accompanying decrease in rectal bleeding subscore of ≥ 1 point or an absolute rectal bleeding subscore of 0 or 1 at Week 10
Induction	Exploratory	Endoscopic response at Week 10	An endoscopic subscore of 0 or 1 at Week 10
Maintenance	Primary	EBS remission at Week 58	An endoscopic subscore of 0 or 1*, rectal bleeding subscore of 0, and at least a 1 point decrease in stool frequency from induction baseline to achieve a subscore of 0 or 1 at Week 58
Maintenance	Key Secondary	6-month corticosteroid-free EBS remission at Week 58	EBS remission with no corticosteroid use for the indication of UC for at least 6 months prior to Week 58 among subjects who are on corticosteroid at re-baseline (baseline of maintenance study). Subjects who weaned off steroids but required re-initiation within 6 months prior to Week 58 assessment will be considered to have not met this endpoint.
Maintenance	Key Secondary	Sustained EBS remission at Week 58	EBS remission at both Week 10 and Week 58
Maintenance	Key Secondary	MCS remission at Week 58	An MCS of 2 or less and no single subscore larger than 1 at Week 58
Maintenance	Key Secondary	An endoscopic subscore of 0 at Week 58	An endoscopic subscore of 0 at Week 58
Maintenance	Key Secondary	Geboes histologic remission at Week 58	Based on the Geboes Scale (Appendix 6), all of the following must be met to be considered in Geboes histologic remission at Week 58: Grade 0 of ≤ 0.3 , Grade 1 of ≤ 1.1 , Grade 2a of $\leq 2A.3$, Grade 2b of 2B.0, Grade 3 of 3.0, Grade 4 of 4.0, and Grade 5 of 5.0.
Maintenance	Key Secondary	MCS remission (alternative definition) at Week 58	Rectal bleeding, stool frequency, and PGA subscore of 0 and an endoscopic subscore of 0 or 1; overall MCS of ≤ 1 at Week 58
Maintenance	Exploratory	6-month corticosteroid-free MCS remission at Week 58	MCS remission with no corticosteroid use for the indication of UC for at least 6 months prior to Week 58 among subjects who are on corticosteroid at re-baseline
Maintenance	Exploratory	Sustained MCS remission at Week 58	MCS remission at both Week 10 and Week 58

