6.6. Change from Protocol-Specified Efficacy Analyses

Protocol amendment 5 (02 April 2019) Section 8.11, described that a review of the results of all primary and key secondary endpoints of Cohort A and B Induction Studies would be performed by a Gilead executive team in parallel with the DMC's review of the end of induction analysis.

However, this review by a Gilead executive team was not performed due to concerns raised by the Voluntary Harmonization Procedure (VHP) during protocol review. No Gilead executive team member or GS-US-418-3898 study team member had access to any unblinded study results prior to study completion and database finalization/lock.

EBS remission (alternative definition), endoscopic response, MCS response, changes from baseline in MCS and partial MCS at Weeks 10 and 58 are included as exploratory endpoints for Cohort A Induction Study, Cohort B Induction Study, and Maintenance Study. The analyses on these endpoints are also included as exploratory analyses.

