Appendix 5. Study Treatment Failure Rules

Study treatment failure rules apply to treatment failure that occurs during the course of the study. Study treatment failure rules will be applied to all efficacy endpoints unless otherwise specified. All efficacy data will be censored (set to missing) after treatment failure criteria are met, regardless of the observed data. Subjects who do not have sufficient measurements after censoring to determine the dichotomized endpoint(s) will be considered non-responder for corresponding endpoint(s). Study treatment failure rules override other data handling rules.

Subjects who have any of the following events will be considered a study treatment failure after the earliest event through the end of the Induction Study (if the event occurred during induction) or through the end of the Maintenance Study (if the event occurred during maintenance), regardless of the actual efficacy data collected. Induction baseline will be referenced when calculating the potentially effective use for induction studies and maintenance baseline (re-baseline) will be referenced when calculating the potentially effective use for Maintenance Study.

1) Potentially effective steroid use

Potentially effective corticosteroids, for the purpose of this SAP, are steroids that may impact disease under study. **Potentially effective steroids** include the following steroids when administered for an indication of UC:

a) Commencement of:

Any steroid administered intramuscularly (IM), intravenously (IV), orally (PO), or rectally (PR) at any dose for 7 or more continuous days

- This rule applies regardless if a change in drug, dose, or route (from IM to IV to PO or PR or vice versa) occurs within the seven continuous days; and it includes oral steroids with intended local actions (eg, budesonide)

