- b) Escalation of concomitant steroid dose above the baseline dose for 7 or more continuous days. The baseline steroid dose is defined as the dose at Day 1 of induction if the escalation occurs in the Induction Study, or Day 1 of maintenance (re-baseline) if the escalation occurs in the Maintenance Study. The prednisone equivalent dose will be used to determine escalation of concomitant systemic steroid dose even if there is a change in drug or route. For steroids with local actions (eg, budesonide or any rectally administered steroid), this rule will apply to scenarios where the post-baseline dose is above the baseline dose via the same drug and the same route for 7 or more continuous days.

Potentially effective steroid use only includes use of steroids administered via routes that are IM, PO, IV, or PR. The below steroids will **not** be considered potentially effective steroids regardless of indication for use:

- i) ocular steroids (ie, eye drops)
- ii) topical steroids (eg, cutaneously applied solely to the skin, or topically applied to the nasal mucosa)
- iii) inhaled steroids (eg, inhalational fluticasone for asthma)
- iv) intra-articular steroids (steroids administered directly into a joint)
- v) neuraxial steroids (steroids administered into the epidural or spinal space)

2) Potentially effective immunomodulator use

Commencement of a different class of oral, IM, SC, or IV immunomodulator drugs (where the subject was not previously taking concomitant immunomodulators of the same class on Day 1 of induction or maintenance), including but not limited to 6-MP, azathioprine, MTX, 6-thioguanine, and prohibited immunomodulators including but not limited to cyclosporine, leflunomide, tacrolimus, thalidomide regardless of dose, for 7 continuous days. The use of an immunomodulator will be considered potentially effective when it is administered for an indication of UC.

3) Potentially effective biologic agent use

Commencement of a biologic agent including but not limited to TNF α antagonists, IL-12/23 antagonists, and vedolizumab (or similar agents), regardless of indication for use and duration.

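### Table 6-1 limits the 6-month corticosteroid-free condition to steroids given for UC, but its denominator takes in anyone on a corticosteroid at re-baseline

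*SAP*

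**What the plan says.** SAP Table 6-1 (Section 6.1) asks for two things, EBS remission and a steroid-free period, the latter worded as "no corticosteroid use for the indication of UC for at least 6 months prior to Week 58 among subjects who are on corticosteroid at re-baseline". The next sentence in the same row adds: "Subjects who weaned off steroids but required re-initiation within 6 months prior to Week 58 assessment will be considered to have not met this endpoint". That sentence names no indication. The exploratory MCS version has the same UC-limited condition and the same unlimited denominator, but no re-initiation sentence.

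The protocol's Definition of Terms reads: "EBS remission with no corticosteroid use for at least 6 months prior to Week 58 among subjects who are on corticosteroid at Baseline". It limits neither side by indication, and it uses Baseline rather than re-baseline.

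SAP Appendix 5 says that potentially effective steroids "include the following steroids when administered for an indication of UC", by the oral, intramuscular, intravenous or rectal route. It then lists products that never count, among them "inhaled steroids (eg, inhalational fluticasone for asthma". That list serves the treatment-failure rule; Table 6-1 does not refer to it.

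SAP 6.6, on changes from the protocol, covers an executive review that was not performed and some added exploratory endpoints ("EBS remission (alternative definition), endoscopic response, MCS response, changes from baseline in MCS and partial MCS at Weeks 10 and 58 are included as exploratory"). It mentions neither the UC limit nor the move to re-baseline.

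SAP 3.5 places the endpoint at H3 (200 mg) and H4 (100 mg), directly after the Maintenance primary. SAP 3.5 and 6.3.2 stop formal testing within a dose at the first failure.

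**The concern.** The endpoint is meant to show remission held for six months without corticosteroids among subjects who were taking them. That requires the steroid that brings a subject into the denominator to be the steroid whose absence is then checked. In Table 6-1 it need not be. A subject on prednisone recorded for asthma is on corticosteroid at re-baseline, has no use for the indication of UC, and if in EBS remission is a corticosteroid-free success while still taking the drug.

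For each dose, five further key secondaries stand behind this one: sustained EBS remission, MCS remission, endoscopic subscore of 0, Geboes histologic remission and the alternative MCS remission. The endpoint is also analysed only in steroid users, so each misclassified subject carries more weight than in the full Maintenance FAS.

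**Working it through.** **1. Case by case on the literal text of the EBS row**

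| Steroid at re-baseline | Later course | In denominator? | Steroid-free in SAP? | Steroid-free in protocol wording? |
|---|---|---|---|---|
| For UC | Continued into the window | Yes | No | No |
| For UC | Weaned, restarted for UC in the window | Yes | No | No |
| For UC | Weaned, restarted for another reason in the window | Yes | No (re-initiation sentence), although the first sentence is met | No |
| Systemic, not for UC | Continued | Yes | **Yes** | No |
| Inhaled or topical, not for UC | Continued | Not settled | Yes, if in the denominator | No, if in the denominator |

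The fourth line is the defect. The third shows the two sentences of one definition disagreeing about non-UC restarts. In the exploratory MCS row, which lacks the second sentence, that third case would count as steroid-free.

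**2. Does another rule close the gap?** Appendix 5 does not: its steroid rule is UC-only. Protocol Table 5-1 restricts non-rectal steroids by dose (above 30 mg/day prednisone equivalent), not by indication. Protocol 5.4.3 does bear on it: from Week 14 all subjects on concomitant steroids must taper until off, with no indication named. From the 30 mg cap at the slowest stated prednisone rate:
- 30 / 2.5 = 12 weeks, and 14 + 12 = Week 26.
- Six months (26 weeks) before Week 58 is Week 32.

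A taper that is followed and succeeds therefore ends before the window opens. The fourth line needs the taper to be read as UC-only or not followed. Such a subject stays in the FAS and is scored as shown.

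**3. The plan's own figures.** Eligible per dose: 0.55 × 520 = 286, split 2:1 into about 191 and 95, matching the stated 285 and 190/95. Power for 40% vs 20% at 2-sided 0.025, with pooled rate 0.333, SE0 = 0.0592, SE1 = 0.0543 and z = 2.241: Φ((0.20 − 2.241 × 0.0592)/0.0543) = 89.2%, or 86.3% with continuity correction. Both agree with the stated figure of more than 85%. No size, rate or power is given for the corticosteroid-free endpoint.

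**4. Size of the subset (assumed).** The share on steroids at re-baseline is not in the documents. At 20%, 30% or 40% of 190/95, the subset is 38/19, 57/28 or 76/38 (filgotinib/placebo). At 57/28 one subject moves the rate by 1/57 = 1.8 or 1/28 = 3.6 points.

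**5. Size of the effect (assumed).** Let m be the share of the subset that continues a non-UC steroid, with EBS remission at the planned 40% and 20%. Successes that an any-indication rule would fail are 0.40m and 0.20m, so the difference rises by 0.20m.

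| m | Rise in difference | Subjects at 57/28 |
|---|---|---|
| 5% | 1 point | 1.1 / 0.3 |
| 10% | 2 points | 2.3 / 0.6 |
| 20% | 4 points | 4.6 / 1.1 |

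**6. Three scorings compared.** Take m = 10% and assume true rates of 30% vs 10% in UC-indicated users.
- SAP as written: 0.9 × 30 + 0.1 × 40 = 31% vs 0.9 × 10 + 0.1 × 20 = 11%; difference 20 points.
- Any-indication condition, as in the protocol: 27% vs 9%; difference 18 points.
- Denominator limited to UC-indicated users: 30% vs 10%; difference 20 points.

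Against the matched denominator, each rate shifts by a point and the difference does not move, because the assumed effect is 20 points in both kinds of user. With other assumptions it could move either way.

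**The case against.** The strongest reply is that the situation should hardly arise. The taper covers all concomitant steroids and would clear prednisone by about Week 26. The SAP elsewhere speaks of oral, systemically absorbed corticosteroids (stratification in 6.2.3) or systemically absorbed corticosteroids (baseline table in 5.2), and protocol 5.4.1 lists oral steroids as allowed medication for UC. On that context the sponsor probably meant UC steroids on both sides. The UC limit also follows the SAP's own convention for steroids and immunomodulators in Appendix 5. The biologic rule there ("or similar agents), regardless of indication for use and duration") is the exception, so it does not show the steroid wording to be an error.

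This stands as an argument about frequency and intent. It does not change what Table 6-1 tells a programmer to do, and nothing in the SAP supplies the missing indication or route.

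Three stronger readings are tempting and are not supported:
- **That a subject who tapers UC prednisone and is then given prednisone for, say, arthritis still counts as steroid-free for EBS remission.** The protocol does note that "Ulcerative colitis may also be associated with extra-intestinal manifestations including ocular lesions, skin lesions, arthritis, and primary sclerosing cholangitis", but the re-initiation sentence names no indication and fails that subject.
- **That inhaled-steroid users are plainly in the denominator.** The row does not say so, and the context points to systemic drugs. It is unsettled.
- **That the wording could flip H3.** At 57/28 an unstratified pooled z-test gives p = 0.0252 for 19 vs 3 responders and p = 0.0174 for 20 vs 3. This shows how fragile any endpoint is in so small a subset. It does not measure this defect.

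**Conclusion.** The mismatch is real on the face of Table 6-1: the numerator is limited to UC-indicated use and the denominator is not. It departs from the protocol definition without being recorded in SAP 6.6. It reaches only subjects whose re-baseline steroid is recorded for a non-UC indication and continues into the window; continuous steroid use for UC fails the endpoint, as it should. For systemic steroids the case also depends on the taper being read as UC-only or not followed.

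The number affected is unknown and probably small. Under the assumptions shown, the literal rule raises the difference by 1 to 4 points over an any-indication rule for m of 5% to 20%, and need not change it against a matched denominator. The reason to act is that this is the first key secondary in Maintenance, the subset is small, and the correction is nearly free.

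A reader might infer that the endpoint fails to answer its objective, or that any-indication use must count as failure in the primary scoring. The documents support neither. The first overstates a rare case. The second is a choice of estimand and, combined with a UC-only denominator, would leave the two sides unmatched.

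**What to change.** Before unblinding, in SAP Table 6-1, for both the EBS and the exploratory MCS versions:

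1. Restrict the denominator to subjects taking corticosteroid for UC at re-baseline by the Appendix 5 routes (oral, intramuscular, intravenous, rectal), and state the same indication and routes in the steroid-free condition.
2. Make the re-initiation sentence consistent with that definition, and state whether it applies to the MCS version.
3. Record in SAP 6.6 both departures from the protocol definition: the added UC limit and the move from Baseline to re-baseline. The second should change few subjects, since steroid doses are to stay stable to Week 14, but it should be on record.
4. Add a sensitivity analysis that counts systemic steroid use for any indication in the 6-month window as not corticosteroid-free.

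The taper text in protocol 5.4.3 and the endpoint text should be reconciled on whether non-UC steroids are meant; no clinical rule is proposed here.

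The cost is SAP wording and programming. Appendix 5 already relies on route and indication, so no new data should be needed. The downside is a slightly smaller denominator.

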6.2. Primary Efficacy Endpoints

6.2.1. Definition of the Primary Efficacy Endpoints

The primary efficacy endpoints are the proportion of subjects achieving EBS remission at Week 10 for the Induction Studies (Cohort A Induction Study and Cohort B Induction Study) and at Week 58 for Maintenance Study as defined in Table 6-1. MCS subscores collected at screening will be used as baseline values for evaluation of EBS remission at both Week 10 and Week 58.

6.2.2. Statistical Hypotheses for the Primary Efficacy Endpoints

The primary efficacy objective of the Induction Studies (Cohort A Induction Study and Cohort B Induction Study) and the Maintenance Study are to evaluate efficacy of filgotinib in establishing EBS remission at Weeks 10 and 58. These objectives are translated into the following primary statistical hypotheses at Weeks 10 and 58:

- H1: The EBS remission rate in the filgotinib 200 mg group is equal to the EBS remission rate in the placebo group.
- H2: The EBS remission rate in the filgotinib 100 mg group is equal to the EBS remission rate in the placebo group.

Each null hypothesis is tested against the alternative hypothesis that the EBS remission rate is different between the respective filgotinib dose group and the placebo group.

6.2.3. Analysis of the Primary Efficacy Endpoint

For the individual Induction Studies (Cohort A Induction Study and Cohort B Induction Study), a stratified Cochran-Mantel-Haenszel (CMH) test will be used to compare the treatment effect between the filgotinib 200 mg group and placebo and between the filgotinib 100 mg group and placebo separately. The CMH tests will be stratified by the following factors:

- Concomitant use of oral, systemically absorbed corticosteroids at Day 1
- Concomitant use of immunomodulators at Day 1
- Exposure to biologic agent as listed in [Appendix 2](#) (≤ 1 , > 1 ; for Cohort B Induction Study only)

For the Maintenance Study, a CMH test will be used to compare the treatment effect between filgotinib 200 mg and placebo among the subjects from the Cohort A and B Induction Studies combined being treated with filgotinib 200 mg. The CMH test will be stratified by the following factors:

- Participation in Cohort A or Cohort B
- Concomitant use of oral, systemically absorbed corticosteroids at re-baseline
- Concomitant use of immunomodulators at re-baseline

Similarly, a CMH test with the same stratification factors will be used to compare the treatment effect between filgotinib 100 mg and placebo among the subjects from the Cohort A and B Induction Studies combined being treated with filgotinib 100 mg.

The stratified CMH chi-square p-value will be provided for each of the above comparison. Strata with low numbers of subjects might be aggregated for the CMH test. The 2-sided 95% confidence interval (CI) of EBS remission rate based on normal approximation method with a continuity correction will be provided for each treatment group. In addition, non-stratified risk difference estimated along with its 2-sided 95% CI using the normal approximation (ie, the Wald method) with a continuity correction for the difference in proportions will be provided. Reference Section 3.5 for the significance level that will be used to declare a statistically significant treatment effect for each filgotinib group. Stratification variables based on the eCRF data will be used for the analysis.

Bar-charts of proportions of subjects achieving EBS remission at Week 10 and Week 58 will be provided by treatment group with corresponding p-values. In addition to the primary analysis method described above, the proportion of subjects in EBS remission who had a stool frequency subscore of 0 versus 1 will be calculated and summarized.

